13.4.2 Statistical Hypothesis, Model, and Method of Analysis

As described in Section 3.5 and 13.8, this study has been designed to detect an increase in the 50% responder rate from a benchmark of 20% to 35%. A one-sample binomial test will test this hypothesis at the 0.1 level of significance.

As a related secondary analysis, seizure frequency will be estimated separately for each patient within the titration, treatment, tapering, and follow-up phases of treatment, and the percent reduction in seizure frequency relative to baseline computed. The distribution across patients within each treatment phase in the percent reduction will be described. Depending upon the distribution of these data, means and standard deviations may be used to describe the distribution of percent reduction or quartiles.

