3.2 Design and Procedure

This is a Phase 4 single-arm study to assess the efficacy of perampanel as an adjunct anti-epileptic in patients with primary glioma that are presenting refractory partial onset seizure activity (defined as 3 or more seizures in a 28-day period). In this study, patients will be started on a dose of 2 mg of perampanel daily taken orally at bedtime for 2 weeks. At the start of week 3 Perampanel will be titrated up in dose in 2mg increments per week up to 8mg daily, as long as it is well tolerated by the patient. The highest dose of perampanel will be 8 mg orally at bedtime. Patients will begin the treatment period of the study starting at week 5 and will continue through the end of week 12. The planned treatment dose is 8mg, but the dose can be modified by the physician based on patient reported tolerability. Patients will be assessed in the Brain Tumor Center Clinic every 8 weeks. Study assessments will be made at enrollment, 8 weeks, 16 weeks, and 24 weeks.

Assessments will include history and physical examination (H&P) including Karnofsky Performance Status (KPS), neurological examination, evaluation of seizure history, patient-reported outcomes of QoL, and neurocognitive testing using CNS Vital Signs®. After a total of 16 weeks of therapy, perampanel will be tapered for 3 weeks and then will be discontinued, such that at week 20, patients will only be taking their original AED regimen. Patients will then be monitored through Week 24. Patients will remain on their original AED therapy during this treatment time and the dose of their original AED regimen at the start of the study will not be changed while they are on study. If seizure control is achieved during the treatment period or if seizures occur during the tapering period, patients can be continued on perampanel per the discretion of the treating physician. In this instance, perampanel will be prescribed by the treating physician and not provided within the confines of the study. Efficacy will be assessed using a log of patient-reported seizure activity. As is standard procedure at the PRTBTC, patients will be given a log to record the number of seizures that occur. Research team members will regularly contact patients for reminders and reports from the log. Safety will be assessed with the following laboratory evaluations: complete blood count (CBC) with differential, complete metabolic panel (CMP), and toxicity assessment.

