Perampanel will be given according to FDA-approved guidelines over a 24-week period. Patients will be started on a dose of 2 mg daily taken orally at bedtime for 2 weeks. At the start of week 3 Perampanel will be titrated up in dose in 2mg increments per week up to 8mg daily, as long as it is well tolerated by the patient. Weeks 1 and 2, patients will take 2mg, Week 3 they will take 4 mg, Week 4 they will take 6mg and starting at week 5 they will take 8mg. Highest dose will be 8 mg orally at bedtime. Starting at week 5, patients will begin the treatment period, which goes from day 1 of Week 5 through day 7 of Week 16. Patients will be assessed in the Brain Tumor Center Clinic every 8 weeks. Assessments will be made at enrollment, 8 weeks, 16 weeks, and 24 weeks. Assessments will include history, physical examination, neurological examination, evaluation of seizure history, patient-reported outcomes of quality of life, and neurocognitive testing using CNS Vital Signs®. After a total of 16 weeks on therapy, perampanel will be tapered down. At Week 17, patients will begin taking 6mg of perampanel, Week 18 4mg, Week 19 2mg, and Week 20 they will no longer take perampanel. Patients will be considered off treatment at the end of week 20, once perampanel has cleared their system. The planned treatment dose is 8mg, but the dose can be modified by the physician based on patient reported tolerability. Titration and taper periods will be determined by the physician in the case where patients do not reach the planned treatment dose of 8 mg daily. Patients will continue to take their original AED regimen after they stop perampanel. Patients will then be monitored through Week 24. Patients will remain on their original AED regimen during this treatment time and the dose of their original AED at the start of the study will not be changed while they are on study. If seizure control is achieved during the treatment period or if seizures occur during the tapering period, patients can be continued on perampanel per the discretion of the treating physician. In this instance, perampanel will be prescribed by the treating physician and not provided within the confines of the study. As is standard procedure at the PRTBTC, patients will be given a log to record the number of seizures that occur. Research team members will regularly contact patients for reminders and reports from the log.

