10.3 Treatment Period

Day 1

- Subjects will be started on a dose of 2 mg of perampanel daily taken orally at bedtime for 2 weeks.
- Subjects will then be titrated up in dose in 2 mg increments each week up to 8 mg daily. Week 3 4mg daily, Week 4 6 mg daily and starting week 5 8 mg daily. The highest dose of perampanel will be 8 mg orally at bedtime.

Week 8 assessments) (+ 1 week)

- History and physical exam, including KPS and a full neurologic assessment, with collection of seizure log (subjects will keep a seizure log throughout the study)
- Toxicity assessment using CTCAE v.4 guidelines (continuous throughout study)
- CBC with diff
- CMP
- Quality of life measurements and neurocognitive testing

Week 16 assessments) (+ 1 week)

- After a total of 16 weeks on therapy, subjects will now be tapered off of perampanel over a period of 4 weeks. Week 17 6mg daily, Week 18 4mg, Week 19 2mg, and at Week 20 they will no longer take perampanel. (
- History and physical exam, including KPS and a full neurologic assessment, with collection of seizure log (subjects will keep a seizure log throughout the study)
- Toxicity assessment using CTCAE v.4 guidelines
- CBC with diff
- CMP
- Quality of life measurements and neurocognitive testing

Week 24 assessments- End of Treatment) (+ 1 week)

- History and physical exam, including KPS and a full neurologic assessment, with collection of seizure log (subjects will keep a seizure log throughout the study)
- Toxicity assessment using CTCAE v.4 guidelines
- CBC with diff
- CMP
- Quality of life measurements and neurocognitive testing
- Toxicity assessment using CTCAE v.4 guidelines (continuous throughout study)

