13.6 Exploratory Objectives

The effect of perampanel on neurocognition and patient-reported outcomes of quality of life will be explored. Mean changes from baseline in neurocognition and QOL subscales will be computed at each follow-up assessment.

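### Follow-up seizure summaries and Week 24 scores pool patients who stopped perampanel with those who continued it off-study because of their outcome, and the plan has no rule to separate them

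*Combined protocol and SAP*

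**What the plan says.** The design stops perampanel after the taper and then observes patients to Week 24. Section 3.2 describes the taper "such that at week 20, patients will only be taking their original AED regimen".

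Sections 3.2 and 7.1 also provide an exception. In the words of 7.1: "If seizure control is achieved during the treatment period or if seizures occur during the tapering period, patients can be continued on perampanel". This is at the treating physician's discretion, with the drug prescribed outside the study supply. Neither section says whether such a patient leaves the study, stops the seizure log or is analysed separately. Table 1 in Section 10 schedules Week 24 assessments without exception, and Section 13.1 puts everyone who completes the treatment period into the efficacy analyses.

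On analysis, Section 13.4.2 says that "seizure frequency will be estimated separately for each patient within the titration, treatment, tapering, and follow-up phases of treatment". The percent reduction from baseline is then described across patients within each phase, by means or quartiles depending on the data. Section 13.6 says: "Mean changes from baseline in neurocognition and QOL subscales will be computed at each follow-up assessment". Neither section splits patients by whether they were still taking perampanel.

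The phase boundary is described in three ways. Section 3.2 has a 3-week taper. Section 10.3 says "subjects will now be tapered off of perampanel over a period of 4 weeks". Section 7.1 adds: "Patients will be considered off treatment at the end of week 20, once perampanel has cleared their system".

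**The concern.** The label of a phase and the treatment state of its patients can differ. By design, follow-up is a period on the original AEDs alone. For a patient who continues by outside prescription it is a period on perampanel. Both routes to continuation depend on seizure outcome, so the mix is not random: patients who did well may stay on drug, and patients whose seizures return in the taper may also stay on or resume it.

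This is a single-arm study, so a reader will naturally take the follow-up column as what happens after perampanel is withdrawn. If it includes well-controlled patients still on drug, the mean reduction can suggest benefit that outlasts treatment when there is none. Patients who resume drug after taper seizures hide later relapse in the same column. The Week 24 mean scores combine the same two states. The unsettled position of week 20 adds a smaller uncertainty about which days belong to which phase.

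**Working it through.** **1. The plan's own figure.** Section 13.4.2: "A one-sample binomial test will test this hypothesis at the 0.1 level of significance". Inputs from 13.8: null rate 0.20, alternative 0.35, 90% power, 61 evaluable patients. Taking the test as exact and one-sided, success at 17 or more responders of 61 gives alpha 0.0879 and power 0.9055. In a scan of n from 50 to 74, 61 is the smallest n with alpha at most 0.10 and power at least 0.90. The figure reproduces and does not depend on anything after the treatment period. Section 3.2 ends that period at week 12 and Section 7.1 at week 16. That is a separate conflict to reconcile, but both ends fall before the taper starts in week 17.

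**2. Who could be on drug in follow-up.** The documents give no continuation rate. If 35% of 61 completers respond and all of them continue, the number is 0.35 × 61 = 21.35, about 21. If 25%, 50% or 75% of responders continue, it is about 5, 11 or 16. Equating seizure control with the 50% responder definition is an assumption; the protocol does not define seizure control.

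**3. Effect on the pooled mean.** Assume 0% reduction in everyone off drug and reduction R in those who continue. Then pooled mean = share continuing × R.

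| Share of all patients continuing | R = 75% | Median | Upper quartile |
|---|---|---|---|
| 10% | 0.10 × 75 = 7.5% | 0 | 0 |
| 20% | 0.20 × 75 = 15% | 0 | 0 |
| 35% | 0.35 × 75 = 26% | 0 | 75% |

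The off-drug value is 0% in every row. The upper quartile moves only when more than 25% of patients continue.

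Sensitivity, as 25% to 100% of responders continue:
- 35% responders, R = 70%: 0.35 × 0.25 × 70 = 6.1% to 0.35 × 70 = 24.5%.
- 35% responders, R = 50%: 4.4% to 17.5%.
- 20% responders, R = 70%: 3.5% to 14.0%.

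**4. The taper-relapse route.** Assume 35% responders at R = 70%. Half of them relapse fully without drug; the other half would keep their reduction off drug. If all stay off drug, the follow-up mean is 0.35 × 0.5 × 70 = 12.25%. If the relapsers resume, it is 0.35 × 70 = 24.5%. Their taper seizures still count in the taper summary.

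**5. Week 24 scores.** Section 5.3 ties seizure control to quality of life, which points towards better scores in continuers. The adverse-event table in 5.2.2 points the other way for some domains (8 mg versus placebo): fatigue 8.4% versus 4.8%, somnolence 15.5% versus 7.2%, irritability 6.7% versus 2.9%. The net direction for cognition, mood and fatigue cannot be settled from the documents.

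**6. Week 20.** Sections 7.1 and 10.3 give the same weekly steps: reduced doses in weeks 17, 18 and 19, and none in week 20. The 3-week description in 3.2 fits those steps. What differs is the 4-week label in 10.3 and the off-treatment point at the end of week 20 in 7.1. Follow-up can therefore be weeks 20–24 (35 days) or 21–24 (28 days). As a deliberately extreme case, take a baseline of 3 seizures in 28 days and 3 seizures after the last dose, all in week 20. The reduction is 1 − (3/35)/(3/28) = 20% on the first reading and 1 − 0 = 100% on the second. Most patients would show a much smaller difference.

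**The case against.** The strongest reply is that pooling is inferred from silence. Continued drug is outside the study's confines, and the authors may have meant these patients to leave follow-up. That is fair, and the plan should say so if it is the intention. But nothing removes them from Week 24 monitoring or the analysis set, so pooling is the default reading. If they did leave, follow-up would lose its well-controlled patients, a different selection that also needs a rule.

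Other points stand in part:
- A reader might infer that taper and follow-up are the only within-patient view without perampanel. They are not: the 28-day baseline is also perampanel-free, and weeks 17–19 are on-drug by schedule for everyone, so continuers differ there only in dose.
- Section 6 sets no objective about lasting benefit, and the summaries are untested. This limits the importance, but the figures will still be reported and read.
- The magnitudes rest on assumed inputs and on the mean. Section 13.4.2 allows quartiles, and the median would not move. Section 13.6, however, specifies means.
- Much of the data exists. Section 7.1 records all concomitant medications, and 7.1.1 provides daily medication logs. Section 13.3 counts perampanel days and tabulates dosing departures, but only through tapering and without splitting outcomes.
- The end-of-week-20 point in 7.1 is a washout definition. A reader might infer a conflict over when dosing stops; the weekly steps do not support that.

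**Conclusion.** The point holds as a gap in two descriptive analyses. As written, the follow-up and Week 24 summaries, and to a lesser degree the late taper, mix patients on and off perampanel who were sorted by outcome. If the drug works and continuers stay in follow-up, mean seizure reduction in follow-up overstates the off-drug state. At 0% reduction off drug and 75% on drug, the excess is 7.5 to 26 percentage points when 10% to 35% of patients continue. The true size is unknown because the continuation rate is unknown.

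A reader might infer that the whole off-drug picture is certainly biased towards lasting benefit, Week 24 cognition and mood included. The documents do not support that: the handling of continuers is unstated and the direction for those scores is uncertain. The primary endpoint, its test and the sample size are not affected.

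**What to change.** - In 13.4.2 and 13.6, keep the overall summary and add taper, follow-up and Week 24 results by actual perampanel status: stopped on schedule, versus continued or restarted off-study. Give the number in each group.
- State whether patients who continue off-study remain in follow-up to Week 24.
- Record start and stop dates and dose of off-study perampanel with the concomitant medications already collected.
- State that both groups are selected by outcome. Results in patients who stopped are descriptive; they do not estimate the effect of withdrawal in all patients, because well-controlled patients and taper relapsers may be missing from that group.
- Reconcile the taper length in 3.2 and 10.3 with the off-treatment point in 7.1, so that week 20 belongs to one named analysis phase.

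The cost is SAP wording, one concomitant-medication entry and an extra column per table. The downside is smaller groups in the descriptive tables.

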5.2.2 Clinical experience

Perampanel is currently FDA-approved for the adjunctive treatment of refractory partial seizures in patient \geq 12 years of age. In a pooled analysis of three phase III studies involving 1,478 patients, median change in partial seizure frequency was greater with perampanel in comparison to placebo.² Specifically, median change in partial seizure frequencies was as follows: perampanel 4 mg, -23.3%; perampanel 8 mg, -28.8%; perampanel 12 mg, -27.2%; and placebo, -12.8%. Moreover, 50% responder rates were as follows: perampanel 4 mg, 28.5%; perampanel 8 mg, 35.3%; perampanel 12 mg, 35.0%; and placebo, 19.0%. In this pooled analysis, perampanel was well tolerated with the most frequent treatment-emergent adverse events (TEAEs) being dizziness, somnolence, and headache. Of note, there were no deaths reported and no clinically meaningful mean change in laboratory values, electrocardiography (ECG) findings, or vital signs.¹⁰ TEAEs from the pooled analysis are listed in the table below for perampanel dose 2 mg to 12 mg and placebo.

Adverse Event, n (%)	Placebo (n=442)	Perampanel 2 mg (n=180)	Perampanel 4 mg (n=172)	Perampanel 8 mg (n=431)	Perampanel 12 mg (n=255)
Any TEAE	294 (66.5)	111 (61.7)	111 (64.5)	350 (81.2)	227 (89.0)
Dizziness	40 (9.0)	18 (10.0)	28 (16.3)	137 (31.8)	109 (42.7)
Somnolence	32 (7.2)	22 (12.2)	16 (9.3)	67 (15.5)	45 (17.6)
Headache	50 (11.3)	16 (8.9)	19 (11.0)	49 (11.4)	34 (13.3)
Fatigue	21 (4.8)	8 (4.4)	13 (7.6)	36 (8.4)	31 (12.2)
Irritability	13 (2.9)	7 (3.9)	7 (4.1)	29 (6.7)	30 (11.8)
Nausea	20 (4.5)	4 (2.2)	5 (2.9)	25 (5.8)	20 (7.8)
Fall	15 (3.4)	2 (1.1)	3 (1.7)	22 (5.1)	26 (10.2)
Nasopharyngitis	18 (4.1)	7 (3.9)	9 (5.2)	23 (5.3)	11 (4.3)
Upper respiratory	12 (2.7)	11 (6.1)	6 (3.5)	14 (3.2)	10 (3.9)

tract infection					
Ataxia	0 (0.0)	0 (0.0)	1 (0.6)	14 (3.2)	21 (8.2)
Balance disorder	2 (0.5)	0 (0.0)	0 (0.0)	22 (5.1)	8 (3.1)

Most TEAEs were mild to moderate and appeared to be dose related. From the pooled analyses, discontinuation of perampanel at 4 mg was 2.9%, at 8 mg was 7.7%, and at 12 mg was 19.2% in comparison to placebo.¹⁰ Common discontinuation TEAEs were dizziness, convulsion, and somnolence.

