7.4 Definition of Evaluable Subjects, On Study, and End of Study

All patients who complete the treatment period will be included in the primary endpoint analysis. All patients who received protocol treatment, regardless of duration, will be included in the safety analysis.

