13.1 Analysis Sets

As indicated in section 7.4, subject to the availability of data, all patients who receive perampanel treatment will be included in safety analyses. All patients who complete the treatment period of the study will be included in efficacy analyses.

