13.5 Secondary Objectives

The percentage of patients with unacceptable adverse events that are possibly, probably, or definitely related to perampanel treatment will be calculated. Unacceptable adverse events include all CTCAE Grade 4 or 5 toxicities that are possibly, probably, or definitely related to perampanel, as well as suicidal ideation (any grade) or suicide attempt (Grade 3-5).

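### No analysis of seizure increase covers all treated patients: the seizure log feeds only efficacy summaries, which Section 13.1 limits to treatment-period completers

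*Combined protocol and SAP*

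**What the plan says.** **Use of the log.** Section 3.2 assigns the patient-reported seizure log to efficacy, and assigns safety to blood count, metabolic panel and toxicity assessment. Section 13.4.1 uses the log for the 50% responder rate. Section 13.4.2 adds a descriptive analysis in which "seizure frequency will be estimated separately for each patient within the titration, treatment, tapering, and follow-up phases of treatment", followed by percent reduction from baseline: "The distribution across patients within each treatment phase in the percent reduction will be described". The summary is by mean and standard deviation or by quartiles.

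**Analysis sets.** Section 13.1: "All patients who complete the treatment period of the study will be included in efficacy analyses". Section 7.4: "All patients who complete the treatment period will be included in the primary endpoint analysis", and for safety, "All patients who received protocol treatment, regardless of duration, will be included in the safety analysis".

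**Safety endpoint.** The Section 6 table counts patients with any adverse event at least possibly attributable to perampanel, at any grade. Section 13.5 is narrower: "Unacceptable adverse events include all CTCAE Grade 4 or 5 toxicities that are possibly, probably, or definitely related to perampanel", plus suicidal ideation or attempt.

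**Why seizures matter as a harm.** Section 5.2.2, on the pooled phase III data: "Common discontinuation TEAEs were dizziness, convulsion, and somnolence". Sections 3.2 and 7.1 also foresee seizures during the taper.

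**The concern.** For an add-on anti-epileptic drug, more seizures on treatment is a harm as well as a lack of benefit. The log measures it directly from the first dose, yet every planned use of the log is an efficacy summary. If Section 13.1 governs, the patients most likely to show an increase (those who worsen and leave) are removed before the log is summarised.

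The safety analysis does not fill the gap. A related worsening of Grade 1 to 3 is not counted under Section 13.5, and a worsening of any grade judged unrelated is counted under neither Section 6 nor Section 13.5. In refractory glioma epilepsy, an increase can readily be attributed to the tumour. The trial could therefore report a favourable responder rate and few unacceptable events without saying how many treated patients had more seizures than before.

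**Working it through.** **1. The plan's own figures.** Inputs from Section 13.8: 20% versus 35%, type I error 0.1, power 90%, 16% early discontinuation. With an exact one-sided binomial test (sidedness is not stated), the smallest adequate sample is 61. The rule is at least 17 responders of 61, with exact type I error 0.088 and power 0.905. Enrolment: 61 × 1.16 = 70.8, so 71. Both planned numbers reproduce.

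**2. Patients outside the log summaries if Section 13.1 governs.**
- Expected non-completers: 71 × 0.16 = 11.4, about 11.
- Expected completers: 71 × 0.84 = 59.6, about 60.
- At the pooled 8 mg discontinuation rate of 7.7% (Section 5.2.2): 71 × 0.077 = 5.5, about 5.

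The documents give no share who stop for worsening seizures, so that number lies between 0 and about 11.

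**3. What the exclusion could hide (illustration).** Assume 6 of 60 completers have increased seizure frequency.
- Completers only: 6/60 = 10.0%.
- All 71, if no non-completer worsened: 6/71 = 8.5%.
- All 71, if all 11 did: (6 + 11)/71 = 23.9%.

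A completer summary cannot distinguish values within 8.5% to 23.9%.

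**4. What the planned statistics show among completers.** Percent reduction can be negative, so increases are in the data. The lower quartile of 60 patients falls at about the 15th lowest value. Six worsened patients lie below it, and how much they worsened does not move it. A mean and standard deviation would move, but would not give a count.

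**5. Where an early leaver with worsening is counted.**

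| Output | Counted? |
|---|---|
| Responder rate (13.4.1) | No |
| Phase summaries (13.4.2) under 13.1 | No, including titration |
| Phase summaries (13.4.2) under 7.4 | Possibly; 7.4 does not exclude them |
| Section 6 safety endpoint | If judged attributable; not identified as seizures |
| Section 13.5 | If related and Grade 4 or 5; not identified as seizures |
| Section 13.3 | Days on drug and dose modifications only; no reason for stopping |

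**6. How often a doubling cut is crossed by chance.** Assumptions, not from the documents: Poisson counts; patient rates gamma-distributed with mean 10 per 28 days and shape 1; no treatment effect. From the documents: entry count of at least 3 in a 28-day baseline, and an 84-day treatment period (Weeks 5 to 16 in Section 7.1; Section 3.2 ends it at Week 12, and the two must be reconciled). In simulation, logged frequency is at least double baseline in about 3% of patients over 84 days and about 6% over 21 to 28 days. Clustered seizures would raise these shares.

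**The case against.** The strongest reply is that these patients are already covered. A reader might infer from Section 13.1 that someone who worsens and stops goes unreported altogether, and the documents do not support that. The safety set is everyone treated. Section 11.1 makes worsening of a pre-existing condition a recordable adverse event from the first dose. Section 12.1 has adverse events tabulated continuously. Section 6 counts any attributable event at any grade. All of this stands. What remains is that the patient becomes one unit in a generic percentage, dependent on a causality judgement and, in Section 13.5, on Grade 4 or 5.

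Four further replies have force:

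- **Section 7.4 limits the completer rule to the primary endpoint**, so the phase summaries might include early leavers. Section 13.1 speaks of efficacy analyses generally and is the more direct reading, but the set is not settled.
- **Section 13.4.2 already covers taper and follow-up**, and patients who reach those phases have normally completed treatment. The gap is therefore mainly in titration and the treatment period.
- **Section 5.2.2 says convulsion**, in a general partial-seizure population. Calling this seizure worsening is an inference, and no rate for glioma follows from it.
- **A single-arm count cannot separate drug from disease.** Active chemotherapy is allowed (Section 7.1) and tumours may progress. This limits the proposed table to description, but it does not justify having no table.

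**Conclusion.** The concern holds in this form: the plan contains no analysis of seizure increase in all treated patients, and on the more direct reading its log-based phase summaries omit everyone who stops before the end of the treatment period. About 11 of 71 patients are affected by the exclusion, if the protocol's 16% discontinuation rate applies. How many of them would have worsened is unknown (0 to about 11), so the documents support no estimate of hidden harm. Nor do they support saying that such patients vanish from the report or that perampanel aggravates seizures in glioma. The primary test and sample size are unaffected. The conclusion rests on Section 13.1 governing the phase summaries. If Section 7.4 governs, early leavers may enter those summaries, but a count of patients with increased seizures is still missing.

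**What to change.** 1. **Reconcile Sections 7.4 and 13.1** so that the completer restriction does not apply to the Section 13.4.2 phase summaries. Run these in all patients who received perampanel, with frequency computed over each patient's logged days up to leaving. Days on perampanel cannot serve as the denominator in follow-up, when no drug is given.
2. **Add to Section 13.5, in the safety set**, a descriptive table for titration, treatment, taper and follow-up: the number and percentage with increased seizure frequency versus baseline (for example at least doubled), with an exact 95% confidence interval and the number of patients with log data in each phase.
3. **Add a listing** of patients who stopped with worsening seizures, showing phase, logged days, baseline and last logged frequency, and recorded reason for stopping.
4. **Label the table as descriptive.** State that some patients cross the cut by chance (about 3% over 84 days and about 6% over 21 to 28 days in the illustration, more with clustering), and that without a control arm it is not a drug-caused harm rate.

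Cost: wording changes, one table and one listing. The log is kept throughout the study, and Sections 10.4 and 10.7.2 ask early leavers to complete visit procedures, so most of the data should exist. Sample size, primary test and clinical management do not change.
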